4.2.3 Follow-Up Phone call/message (POD 1, POD 2 and POD 3)

Phone call to patient to collect additional data on opioid use following discharge, on POD 1, POD 2 and 3 after surgery

4.2.4 Postoperative Visits

Patients will present to postoperative visit #1 of POD 7 per standard of care, at which point VAS pain, ROM, and strength will be assessed.

4.2.5 Withdrawal/Early Termination Visit

Subjects may discontinue their participation in the study at any time. As there is only a single intervention, and the safety of this is not in question, further follow up will not be required if a subject decides to terminate their participation in the study.

4.3 Concomitant Medications, Treatments, and Procedures

All concomitant prescription medications taken during study participation will be recorded on the case report forms (CRFs). For this protocol, a prescription medication is defined as a medication that can be prescribed only by a properly authorized/licensed clinician. Medications to be reported in the CRF are concomitant prescription medications, over-the-counter medications and non-prescription medications.

5 Risks and Benefits

5.1 Potential risks

Medication and Procedure

CONFIDENTIAL

This material is the property of the NYU School of Medicine and Langone Medical Center. Do not disclose or use except as authorized in writing by the study sponsor

The potential risks associated with bupivacaine include neurologic and cardiac toxicity, if injected intravascularly. However, the risk is very low because a trained anesthesiologist using ultrasound guidance will perform both the IPACK block and ACB. US guidance allows the anesthesiologist to see and avoid blood vessels when administering the medication. Additionally, the syringe of the local anesthetic will be aspirated prior to injection by the anesthesiologist and surgeon to ensure that the block needle tip is not intravascular.

The risk of nerve injury or intravascular injection in the IPACK block is similar to the standard ACB arm of the study. Risk of infection at the injection site due to the expertise of the anesthesiologist performing the block under ultrasound guidance under sterile conditions to avoid infection risk. Allergic reactions to local anesthetic is possible however, any subjects with a history of allergies to local anesthetic will be excluded from the study.

At the time of the nerve block, the anesthesiologist who is providing the injection under ultrasound will monitor the subject's vitals, respiratory and cardiac status to assess for the aforementioned risk of neurologic or cardiac toxicity, as suggested in the Bupivacaine package insert. Subsequently, patients will be monitored in the post anesthesia care unit per standard of care for any adverse effects of the nerve block including nausea, vomiting, blurred vision, and infection at the injection site. Both the ACB and ACB plus IPACK block are used as standard of care at this institution depending on treatment physician's preference.

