7.4 Time Period and Frequency for Event Assessment and Follow-Up

The occurrence of an AE or SAE may come to the attention of study personnel during study visits and interviews of a study participant presenting for medical care, or upon review by a study monitor. All AEs including local and systemic reactions not meeting the criteria for SAEs will be captured on the appropriate RF. Information to be collected includes event description, time of onset, clinician's assessment of severity, relationship to study product (assessed only by those with the training and authority to make a diagnosis), and time of resolution/stabilization of the event. All AEs occurring while on study must be documented appropriately regardless of relationship. All AEs will be followed to adequate resolution.

Any medical condition that is present at the time that the participant is screened will be considered as baseline and not reported as an AE. However, if the study participant's condition deteriorates at any time during the study, it will be recorded as an AE. UPs will be recorded in the data collection system throughout the study.

Changes in the severity of an AE will be documented to allow an assessment of the duration of the event at each level of severity to be performed. AEs characterized as intermittent require documentation of onset and duration of each episode.

The PI will record all reportable events with start dates occurring any time after informed consent is obtained until 7 (for non-serious AEs) or 30 days (for SAEs) after the last day of study participation. At each study visit, the investigator will inquire about the occurrence of AE/SAEs since the last visit. Events will be followed for outcome information until resolution or stabilization.

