7.6 Safety Oversight

It is the responsibility of the Principal Investigator [name], and co-investigators [name] MD and [name] MD to oversee the safety of the study at his/her site. This safety monitoring will include careful assessment and appropriate reporting of adverse events as noted above, as well as the construction and implementation of a site data and safety-monitoring plan. Adverse Events such as development of an allergy to local anesthetic, inadvertent intravascular injection of local anesthetic and infection at site of injection will be reviewed every three months. Serious adverse events are rare and are unlikely to occur but if a serious adverse event occurs, steps will be taken to address it. Study recruitment will cease temporarily while a data safety monitoring team convenes to review the event. Medical monitoring will include a regular assessment of the number and type of serious adverse events.

Data Safety Monitoring Plan

The principal investigator [name], and co-investigators [name] MD and [name] MD are responsible for data safety and monitoring of the overall study.

The following data points and outcomes will be reviewed during data safety monitoring reviews: number of patients enrolled, pain scores of patients, AEs and SAEs such as neuro and cardiotoxicity. Data will be monitored quarterly and will be reported at the time of continuing review.

The stopping rules for the study are adverse harm to patients, as measured by the serious adverse events, specifically neurotoxicity, cardiotoxicity, or allergic reaction to bupivacaine. A chi-square test will be used to determine if there is a statistically significant difference ($p<0.01$) in the rate of SAEs between treatment arms. If there is a statistically significant difference in the rates of SAEs between arms, accrual to the trial will be suspended while the study team and data safety monitoring team conduct an evaluation of the events.

The PI will oversee all study activities including data collection and management and will ensure study personnel conduct this study based on the approved protocol.

8 Source Documents and Access to Source Data/Documents

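### Nerve injury and injection-site infection are named block risks, but no AE question is specified between PACU discharge and POD 7, although three contacts take place in that interval.

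*Combined protocol and SAP*

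**What the plan says.** **Risks named.** Section 5.1 states: "The risk of nerve injury or intravascular injection in the IPACK block is similar to the standard ACB arm of the study". Its next sentence, which has lost its verb, names the second risk: "Risk of infection at the injection site due to the expertise of the anesthesiologist".

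**Where they are looked for.** Section 5.1 says that "patients will be monitored in the post anesthesia care unit per standard of care for any adverse effects of the nerve block including" four examples. Infection is one of them and nerve injury is not, and no later setting is given.

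**Contacts after discharge.** Section 4.2.3 reads: "Phone call to patient to collect additional data on opioid use following discharge, on POD 1, POD 2 and 3 after surgery". Section 2.1 adds a VAS score at 24, 48 and 72 hours and allows an email survey in place of the call. Section 4.2.4 lists VAS, range of motion and strength at POD 7.

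**AE inquiry.** Section 7.4 says: "At each study visit, the investigator will inquire about the occurrence of AE/SAEs since the last visit". It also requires all AEs on study to be documented, whatever their relationship to treatment.

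**Oversight.** Section 7.6 gives examples of the AEs to be reviewed: "development of an allergy to local anesthetic, inadvertent intravascular injection of local anesthetic and infection at site of injection will be reviewed every three months". The stopping rule rests on SAEs, "specifically neurotoxicity, cardiotoxicity, or allergic reaction to bupivacaine".

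**The concern.** The only block-specific monitoring described is in the PACU, before the patient leaves after an outpatient procedure. I assume, since the documents do not say so, that infection from that day's injection would rarely show before discharge, and that a new deficit is hard to tell from expected numbness while the block is working. On that assumption the PACU is a poor place to find either of the two local risks.

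The study then speaks to, or surveys, every patient three times in the next three days, and as specified does not ask. New weakness, lasting numbness or an early infection would first be asked about by recall at POD 7. Two declared secondary endpoints are also affected: reaction to the IPACK block (Protocol Summary and 6.2) and incidence of postoperative complications (Protocol Summary only). Neither has a definition, instrument or time point.

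**Working it through.** The plan gives no figure on this point to reproduce, so the check is mainly to set the sections side by side.

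**1. Does the 7.4 inquiry reach POD 1-3?**

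| Contact | Section | Called a visit? | Content listed |
|---|---|---|---|
| Screening | 4.2.1 | Yes | History, eligibility |
| Day 0, including PACU | 4.2.2 | Yes | Pain assessments, vital signs, opioid use |
| POD 1, 2, 3 | 4.2.3, 2.1 | No: phone call, message or email survey | Opioid use, VAS |
| POD 7 | 4.2.4 | Yes | VAS, range of motion, strength |

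Section 4.2.5 also carries the word visit, but requires no further follow-up after withdrawal. On the natural reading, the 7.4 question falls on Day 0 and POD 7. The text does not exclude the POD 1-3 contacts; it simply does not say. An email survey asks only the items that it contains.

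**2. Where is each risk named?**

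| List | Open or closed | Infection | Nerve injury |
|---|---|---|---|
| PACU monitoring, 5.1 | Open | Named | Not named |
| Three-monthly AE review, 7.6 | Open | Named | Not named |
| Data safety review items, 7.6 | Open | Not named | Not named |
| Stopping events, 7.6 | Closed | Not named | Not named |

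**3. Does neurotoxicity cover nerve injury?** Section 5.1 ties neurologic toxicity to intravascular injection of bupivacaine and deals with nerve injury in a separate sentence. Section 7.6 uses neurotoxicity without defining it. Either reading is possible.

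**4. What else would catch an event?** Section 7.4 requires documentation of every AE that comes to notice, and recording continues for 7 days (non-serious) or 30 days (SAEs) after participation ends. Chart review is not a stated safety net: 3.4 describes one post-surgery access to records, the last, for items such as PACU opioid use, and lists no events after discharge. The three-monthly review can act only on what has been captured.

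**5. What can 50 per arm show?** The documents give no rates, so I take 0.5% to 5% as an assumed range. The chance of at least one event among 50 patients is 1 - (1 - p)^50:
- p = 0.5%: 22%
- p = 1%: 39%
- p = 2%: 64%
- p = 5%: 92%

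If none is seen in 50, the one-sided 95% upper limit is 1 - 0.05^(1/50) = 5.8%. Few events are expected, so each one that is caught carries weight.

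The between-arm SAE comparison in 7.6 (chi-square, p<0.01) does not make up for late ascertainment. With no events in the other arm at full enrolment:
- 6 vs 0: 100 × (6 × 50)² / (6 × 94 × 50 × 50) = 6.38, p = 0.0115
- 7 vs 0: 100 × (7 × 50)² / (7 × 93 × 50 × 50) = 7.53, p = 0.0061

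It takes 7 vs 0 to cross the threshold, or 8 vs 0 with continuity correction (p = 0.0099).

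**The case against.** The plan is less bare than its schedule suggests. The PACU list and the three-monthly list are introduced as examples, so nerve injury is unnamed there but not excluded. Section 7.4 captures all AEs, local reactions included, and its POD 7 question looks back over the whole interval, at a visit where strength is tested. Persistent or significant disability is an SAE under 7.1, and under 7.6 an SAE pauses recruitment whether or not it is on the stopping list. The survey, the CRF and the site safety-monitoring plan mentioned in 7.6 are not in the documents and may already hold AE items. Section 6.2 even lists strength at 6 months, although 3.5 ends participation at seven days and 4.2 schedules no such visit.

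Most of this stands. It makes the problem one of timing and of an unspecified inquiry, not of proven loss. It does not supply a question at POD 1-3, and if the investigators intend one, the protocol should say so.

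Three stronger readings are tempting, and the documents support none of them:
- A reader might infer that under-detection makes IPACK look safer, because the experimental arm has one more injection. Follow-up is specified identically in both arms, 5.1 describes the nerve-injury risk as similar, and there are no figures on event rates or detection by arm.
- A reader might infer that the quarterly review ignores nerve injury. Its lists are open, and it covers AEs and SAEs in general.
- A reader might count the days without a question, or the lists that omit nerve injury, as the size of the problem. Neither count measures missed events.

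**Conclusion.** The point holds as a gap in specified ascertainment. Two block risks that the protocol itself names have no specified inquiry from PACU discharge to POD 7, while three contacts pass in that interval. This rests on reading study visit in 7.4 as 4.2 uses the word; if the POD 1-3 contacts were meant to count, the gap is one of wording and the same edit closes it. Separately, nerve injury is a named risk but not a named monitored event, and its relation to neurotoxicity is undefined.

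The consequence is delayed, recall-based detection and weak ascertainment for two declared secondary endpoints. Its size in events cannot be given. This is a cheap improvement worth making. It does not threaten the primary comparison, and it is not evidence that either arm's safety would be misreported in a known direction.

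**What to change.** - **4.2.3 and 2.1:** add the same short AE items to the POD 1, 2 and 3 call or survey in both arms: new or persistent numbness or weakness in the leg or foot, redness or drainage at any injection site, and any unplanned care. Word them identically in both arms, so that they give no hint of the number of injections.
- **7.4:** state that the AE/SAE inquiry applies to these contacts as well as to visits.
- **5.1:** say that ascertainment of infection and nerve injury runs through POD 7, and repair the incomplete sentence on infection.
- **7.6:** name nerve injury among the AEs reviewed every three months.
- **5.1 and 7.6:** reconcile the two on whether neurotoxicity includes nerve injury. No new stopping event is proposed here; which events belong in that rule is for the investigators to decide.

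**Cost.** A few extra questions on contacts that already happen, someone to read the survey answers, minor protocol and CRF wording, and slightly more non-serious AEs to record. One side effect needs care: 6.5 discloses allocation to the patient after a drug-related AE, so earlier questions could bring some disclosures into the days when opioid use and VAS are being reported. Asking the AE items after those two at each contact protects at least that contact's answers.

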5.2 Potential benefits

Study subjects may experience better pain control, improved satisfaction, decreased need for opioids and reduced incidence of side effects. If the study is not inconclusive, the study's results may benefit future patients by showcasing that addition of IPACK block improves pain control in the first 24 hours of an ACLR.

6 Statistical Analysis

6.1 General Approach

The primary analysis will follow the intention-to-treat (ITT) principle in order to evaluate the true outcome of the intervention as experienced by the patient who is blinded to the intervention.

Continuous and categorical baseline characteristics will be compared using Hedges standardized difference. Normally distributed data will be compared using t tests while non-normally distributed continuous outcomes will be assessed using the Mann-Whitney U test.

It is anticipated that the data for some subjects will be incomplete for various reasons: missing diary entries, refusal to answer a question on the questionnaire, onset of illness, loss-to-follow-up, etc. All occurrences of incomplete data will be investigated to carefully document the reasons for the missing data. If the primary outcome (amount of opioid utilization for the first 24 hours after surgery) cannot be ascertained with a reasonable degree of certainty, the patient will be excluded from the study.

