TREATMENT PHASE:

Patients in both the study and control group will receive the standard of care adductor canal block. This consists of 15mL of bupivacaine (0.25%) Injected under ultrasound guidance in the saphenous nerve via the adductor canal. Patients in the study group will receive the additional IPACK block performed using 20 mL of bupivacaine (0.25%) injected into the interspace between the popliteal artery and capsule of the knee.

[figure not shown]
POST-OPERATIVE PHASE:

After initial recruitment, subjects' pain will be assessed via visual analog scale (VAS) by nursing staff during the post-operative period as per standard of care in the post anesthesia care unit, and by the research staff prior to leaving the surgical center. The VAS pain scores are collected and documented in the patient's electronic medical record. Additionally, a standardized regimen of pain medication will be given to all subjects who are enrolled. The pain medications given to patients are standard of care medication 325-5 mg Percocet and vary based on pain level. This is determined by the clinical staff caring for each patient. While the patient is in the PACU prior to discharge, an authorized research member will visit the patient and obtain a pain score using the VAS and McGill Pain Scale. Data on PACU opioid use documented in the electronic medical record will be collected. On POD1, POD 2 and POD 3, a phone call or email survey will be sent to the patient to collect additional data on opioid use at home as well as a VAS score at 24, 48, and 72 hours after surgery.

CONFIDENTIAL

This material is the property of the NYU School of Medicine and Langone Medical Center. Do not disclose or use except as authorized in writing by the study sponsor

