3.6 Total Number of Participants and Sites

Recruitment will end when 100 participants have been enrolled. It is expected that there will be subjects enrolled who will be lost to follow up and be evaluated by intention-to-treat. The sites for enrollment will be the NYU Langone Orthopedic Hospital and NYU Ambulatory Surgery Center at 38th street.

CONFIDENTIAL

This material is the property of the NYU School of Medicine and Langone Medical Center. Do not disclose or use except as authorized in writing by the study sponsor

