3.7 Participant Withdrawal or Termination

Participants are free to withdraw from participation in the study at any time upon request. An investigator may terminate participation in the study if:

- Any clinical adverse event (AE), laboratory abnormality, or other medical condition or situation occurs such that continued participation in the study would not be in the best interest of the participant
- The participant meets an exclusion criterion (either newly developed or not previously recognized) that precludes further study participation

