4.2.2 Enrollment/Baseline

Enrollment/Day of surgery (Visit 1, Day 0)

- Obtain informed consent of potential participant verified by signature on study informed consent form.
- Verify inclusion/exclusion criteria.
- Complete baseline global health and pain assessment
- Randomize to ACB or ACB + IPACK group
- Perform surgery with analgesic intervention determined by randomization
- Record vital signs, opioid usage, results of examinations, other pain assessments.
- Continue observation in PACU preceding discharge, including administration of VAS scores, pain questionnaire, and opioid usage monitoring.

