6.3 Sample Size

Using a 2-sided, 2-sample t test, an α value of 0.05, a power analysis revealed that 42 subjects were needed per group to detect a moderate effect size with a power of 0.80. We chose to enroll 50 subjects per arm to allow for potential dropout and an increased power.

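### Section 6.1 declares an ITT primary analysis but removes randomised patients whose primary outcome is uncertain, by an undefined judgement not said to be masked

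*Combined protocol and SAP*

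**What the plan says.** Section 6.1 opens with: "The primary analysis will follow the intention-to-treat (ITT) principle". The same section expects incomplete data and names causes: "missing diary entries, refusal to answer a question on the questionnaire, onset of illness, loss-to-follow-up, etc". It requires the reasons to be documented. It then deals with the primary outcome, given there as opioid use over the first 24 hours: where that outcome "cannot be ascertained with a reasonable degree of certainty, the patient will be excluded from the study".

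Section 3.6 takes the other line and expects "subjects enrolled who will be lost to follow up and be evaluated by intention-to-treat".

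Consent and randomisation take place on the day of surgery (3.4, 4.2.2), so anyone removed under 6.1 has already been randomised. Part of the outcome is in hand by discharge. Section 4.2.2 lists for that day: "Record vital signs, opioid usage, results of examinations, other pain assessments". Section 2.1 adds: "Data on PACU opioid use documented in the electronic medical record will be collected". Use at home comes from a phone call or email survey on POD 1 to 3 (2.1).

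Section 6.3 gives 42 per group for 80% power and continues: "We chose to enroll 50 subjects per arm to allow for potential dropout and an increased power". Nothing in the document defines a modified ITT set, an imputation method or a missing-data sensitivity analysis for the primary outcome.

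**The concern.** The two instructions cannot both be followed for a patient who is randomised, treated and then gives no usable home report. Section 3.6 keeps that patient and 6.1 removes them. The rule that would operate is the exclusion, so the analysis described as ITT is in fact a complete-case analysis.

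Three features make this more than loose wording:

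- The threshold for adequate certainty has no criterion and no named assessor. Only patients are described as blinded, so the person deciding may know the arm.
- The wording removes the patient from the study, not from one comparison. Read literally, secondary and safety summaries could lose them too.
- Day-of-surgery and PACU opioid doses, which are part of the primary endpoint in 6.2, are discarded with the patient.

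At stake are the protection that randomisation gives the primary comparison and, if heavy users are the ones who go missing, the size of the estimated benefit.

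**Working it through.** **1. The text.** A patient lost before the POD 1 report meets both rules: loss to follow-up is one of 6.1's own causes of incomplete data, and 3.6 assigns such patients to ITT. On the 24-hour window in 6.1 and 6.2, a patient lost later still has a primary outcome, so the direct conflict concerns patients without a usable POD 1 report. On the 72-hour window in the Protocol Summary and 1.3, POD 2 and POD 3 reports matter too and the conflict is wider.

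**2. The plan's own figure.** Section 6.3 gives no number for its moderate effect. The normal formula n = 2(1.960 + 0.842)²/d² at d = 0.62 gives 15.70/0.3844 = 40.8. The t test needs slightly more, 41.8, hence 42. The implied effect is therefore about 0.62 SD. (At d = 0.5 the t test would need 64.) Since 42/50 = 0.84, enrolling 50 covers a loss of up to 16% with power still at 80%. Power with all 50 per arm is about 87%.

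**3. When exclusion biases.** Let Y be opioid use with mean 0, p(Y) the chance of exclusion and r its average. Among retained patients the mean is

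E[Y(1 − p)]/(1 − r) = −Cov(Y, p)/(1 − r).

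- If p does not depend on Y, the covariance is zero in each arm. Even unequal rates then leave the comparison unbiased.
- If p depends on Y identically in both arms, the two shifts cancel under the null. Under a real benefit, controls use more opioid, lose more high users, and the difference shrinks.
- Bias under the null remains only when p depends on Y and its rate or strength differs by arm.

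**4. Size.** Every rate and slope below is an assumption; the documents give none. Simulation: control N(0,1), IPACK N(−0.62,1) or N(0,1) under the null, 50 per arm, logistic exclusion on Y, two-sample t test. Slope 1 means the odds of exclusion rise e-fold per SD of opioid use.

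| Exclusion (control / IPACK) | Estimate (SD) | Power | Null rejection |
|---|---|---|---|
| 16% / 16%, unrelated to use | 0.62 | 80% | 5% |
| 16% / 4%, unrelated to use | 0.62 | not reported | 5.0% |
| Same mechanism, slope 1 (16% / 9.9%) | 0.57 | 78% | 5.0% |
| 16% / 4%, slope 1 in both | 0.52 | 70% | 7.8% |

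Equal rates in both arms, slope 1 in control and 0 in IPACK:

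| Rate in each arm | Estimate (SD) | Null rejection |
|---|---|---|
| 2% | 0.60 | 5.1% |
| 5% | 0.57 | 5.5% |
| 10% | 0.53 | 7% |
| 16% | 0.48 | 10% |

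Power at 5%, 10% and 16% is 79%, 71% and 60%. With selection in the IPACK arm only at 16%, the estimate is inflated to 0.76 SD and null rejection is again about 10%, nearly all of it falsely favouring IPACK.

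**5. Does imputation help?** In the equal-16% case, imputing home use from arm and pre-discharge dose moved the estimate from 0.48 to 0.55–0.58 SD and null rejection from 10.4–10.7% to 5.5–7.1%. This assumed that the pre-discharge share of variance and its correlation with home use were both 0.3 or both 0.5, with half the effect before discharge. With both at 0.1 and the whole effect after discharge, the gain was small: 0.48 to 0.50 SD, and 10.6% to 9.1%.

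**The case against.** The best defence is that ITT in 3.6 means only analysis in the assigned arm wherever an outcome exists, with 6.1 as an ordinary available-case rule. That softens the conflict but does not remove it: 6.1 excludes from the study, and 3.6 speaks of the very patients whose outcomes are missing. The plan also documents reasons for missing data and enrols 50 rather than 42. Both are useful; neither corrects selection.

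The defence is stronger on size. A reader might infer that the block itself will drive exclusions in one arm. Reaction to the IPACK block is an endpoint, illness is a listed cause of missing data, and 3.7 lets an investigator end participation if "Any clinical adverse event (AE), laboratory abnormality, or other medical condition or situation occurs such that continued participation" would not serve the patient. But 5.1 describes nerve-injury and intravascular-injection risk as similar to the ACB arm, and home reports come from blinded patients. The documents leave differential exclusion possible; they do not predict it.

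A reader might also infer that unequal exclusion counts alone prove bias, or that any exclusion dilutes the effect. Neither holds: loss unrelated to opioid use costs only precision. Equally, balanced counts do not rule bias out.

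Finally, 16% is the whole margin between 42 and 50, part of which 6.3 assigns to extra power. It is not a forecast of missing 24-hour data.

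**Conclusion.** Wrong as written, and it should be fixed. The contradiction stands on the text alone: a stated rule in 6.1 defeats the analysis set that 6.1 and 3.6 declare, and no other section reconciles them.

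The statistical harm is conditional. If exclusion depends on opioid use and does so differently by arm, type I error rises: slightly at 2% to 5% exclusion (about 5.1% to 5.5%), and to about 10% only in an upper-end case with 16% excluded in each arm and selection confined to one. If the dependence is the same in both arms, there is no null bias, but a real benefit is understated. If there is no dependence, only precision is lost, and 50 per arm absorbs that up to 16%. These figures rest on normal outcomes, a 0.62 SD effect and assumed exclusion rates and slopes. The documents do not support a claim that the trial will be biased; they support the claim that nothing prespecified protects it.

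**What to change.** Replace the exclusion sentence in 6.1 with:

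> All randomised patients are kept in the ITT set and analysed in their assigned arm, including those whose participation is ended under 3.7 (using data collected up to that point unless use is not permitted). Missing post-discharge opioid use is multiply imputed from arm, baseline VAS, recorded day-of-surgery and PACU opioid dose and any available home reports, by a method suited to the distribution and to the test used. Whether a home report is usable is judged by a written criterion, masked to arm. Missingness and its reasons are reported by arm. Complete-case and delta-adjusted analyses are sensitivity analyses.

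The cost is SAP wording and modest extra analysis, with no new patient contacts and no change in sample size. One practical point: the chart extraction in 3.4 names only PACU opioid use, so it should be confirmed that the intraoperative dose is captured. The primary endpoint in 6.2 needs it in any case.

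The downside is reliance on an imputation model. It removes only part of any selection, and little if pre-discharge use predicts home use poorly, which is why the delta-adjusted analysis is needed. The check in step 5 used arm and pre-discharge dose only, not the full predictor list. The 24-hour versus 72-hour primary window must be reconciled separately, because it decides which home reports are required.
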